## STUDY SUMMARY

TITLE	Passive evaluation in operational environment of the AI Clinician decision support system for sepsis treatment
DESIGN	Prospective multi-centre observational study in 4 ICUs from 2 different NHS Trusts.
AIMS	Confirm operational robustness and technical reliability of the AI Clinician software when operating in real-time in an operational ICU environment.
OUTCOME MEASURES	System / usability data; anonymised patient time series data; doses of treatment chosen by clinicians; assessment data by human evaluators.
POPULATION	Patients: adult patients in intensive care; human evaluators: ICU doctors of any grade.
ELIGIBILITY	Adult patients with sepsis in intensive care
DURATION	Up to 24 months.

## 1. INTRODUCTION

### 1.1. BACKGROUND

Sepsis is life-threatening organ dysfunction due to severe infection and affects 250,000 patients annually in the UK (pre-COVID-19), of whom 48,000 die. In addition, virtually all COVID-19 intensive care unit (ICU) deaths had sepsis. It is a leading cause of death and the most expensive condition treated in hospitals. It was recognised as a top research priority by the James Lind Alliance, a partnership of patients and clinicians to prioritise the most pressing unanswered questions facing the NHS.

The cornerstone of sepsis resuscitation is the administration of intravenous fluids and/or vasopressors (drugs that squeeze the blood vessels to increase blood pressure) to maintain blood flow to prevent organ failure. However, there is huge uncertainty around the individual dosing of these drugs in an individual patient, partially due to high sepsis heterogeneity. The current guidelines provide recommendations at a population-level but fail to individualise the decisions. Wrong decisions lead to poorer outcomes and increased ICU-resource use. A tool to personalise these medications could improve patient survival.

We have developed a new method to automatically and continuously review and recommend the correct dose of these medications to doctors, which was created using artificial intelligence (AI) techniques applied to large medical databases. The method we used is called reinforcement learning. In this framework, we model patients with sepsis in the ICU as belonging to a large number of possible disease states, and we analyse what interventions are likely to help them transition to healthier states, and

eventually to survival. We demonstrated in our initial publication that the value of the AI selected strategy was on average reliably higher than human clinicians. In a large validation cohort independent from the training data, mortality was lowest in patients where clinicians' actual doses matched the AI decisions: mortality rates rose, in a dose dependent manner, as the clinicians' actual decisions diverged from the AI decisions. We have estimated that our AI algorithm could reduce mortality by 10% (in relative terms), which represents over 1,000 lives saved annually in the UK and would scale to hundreds of thousands of lives worldwide. Now, we intend to start clinical testing of this AI technology in the UK.

The envisioned end-product will be a piece of software that will be accessible by clinicians (ICU doctors initially, then eventually to ICU nurses as well) at the bedside in intensive care. This software will be connected to the electronic patient record, which will be fed to the AI algorithm. In return, the AI will identify where the patient sits in the array of possible disease states, and which actions (a dose of intravenous fluids and vasopressors) are most likely to be beneficial.

First, we will develop this software tool, capable of processing patient data within the electronic patient record of NHS hospitals in real-time to suggest a course of action. We will start by evaluating and refining this tool in simulation studies. We will then test the AI tool in two NHS Trusts in a "shadow mode" when the result is **not** provided to duty clinicians in charge of patient care (**the purpose of this application**). This will allow comparison of actual decisions made and recommended decisions from the AI system. Later on (**this is not the purpose of this application**), in the second stage of the clinical evaluation, we will display the recommendations to clinicians to assess the acceptability of the tool to clinicians and also confirm the technical feasibility to inform future large scale clinical trials.

The long-term expected benefits of this project are numerous: improved patient survival, reduced use of precious intensive care resources and reduction in healthcare costs.

## 1.2. RATIONALE FOR CURRENT STUDY

### Research question:

How well does our real-time AI-based system for fluid and vasopressor therapy for sepsis in the ICU perform in an operational clinical environment?

### Hypotheses:

- We are able to run the system with high availability, reliability and acceptable lag (near real-time) at the bedside.
- The quality of AI suggestions, assessed by off-duty clinicians, is appropriate.
- Patients' outcomes are better when actual doctors' decisions match the suggested AI decisions (which remain hidden from on duty doctors).

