## 2. STUDY OBJECTIVES

### Primary objective:

- Confirm operational robustness and technical reliability of the software when operating in real-time in an operational ICU environment. We will measure indicators of system reliability and availability (e.g. what percentage of time is the system available, at different times of the day and night, on weekdays versus weekends, etc.) and the lag of the system (e.g. delay between data recorded at the bedside and model producing an output).

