## 3. STUDY DESIGN

This study is a prospective multi-centre observational study that will include four intensive care units from two different NHS Trusts.

The duration of the study will be up to 24 months.

We will include 100 to 300 adult patients with early sepsis in ICU (within 24h of ICU admission). This number is a pragmatic, realistic estimate of how many patients will satisfy the inclusion criteria in the study period (assuming a conservative 60 admissions per month on each unit (reality is closer to 80-100 pre-COVID-19), and 20% sepsis at admission), and will allow us to deliver on the study objectives.

With regards to human assessors, we will include 6 to 15 ICU doctors, mixing senior registrars, ICU fellows and consultants.

The “system” will be a purpose built webapp accessed from a dedicated laptop, connected to an NHS ICT server, with secure login. It will be linked to a duplicate of the Philips ICCA database (Imperial College Healthcare NHS Trust) or the EPIC EHR (UCLH) which contains ICU patient data in near real time (estimated lag of 5 to 15

minutes). The system will be running the AI Clinician algorithm, which processes ICU patient data and outputs a suggested dose of intravenous fluids and vasopressors. Four times a day (every 6 hours), the system analyses newly admitted ICU patients and identify those who fulfil the sepsis-3 criteria. If they do, they will be added to a list of patients for potential inclusion that will be accessible from within the software (and assessed by human evaluator for enrolment).

The system will contain several tabs:

- 1- **Patient screening.** It displays a list of patients screened and highlighted by the system as fulfilling sepsis-3 criteria. The user (human evaluator) has the option to include them into the study, after verification of the inclusion/exclusion criteria (see sections 4.2 and 4.3 for these criteria).
- 2- **Individual patient data.** This screen contains a drop-down list of patients included in the study. After selecting one, the data time series of this individual patient are displayed here, along with the doses of fluids and vasopressors actually given by human “on-duty” doctors and nurses.

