## 7. STATISTICS AND DATA ANALYSIS

Data and all appropriate documentation will be stored for a minimum of 10 years after the completion of the study, including the follow-up period.

Data of interest	Statistical analyses
-------------------------	-----------------------------

System / usability data	Simple descriptive statistics (e.g. average system lag, number of technical issues per week...)
Anonymised patients' data	Simple descriptive statistics of the patient characteristics. Comparison of the training and prospective cohorts (simple parametric and non-parametric tests comparing demographics, severity of illness, etc).
Evaluators' data (the doctors assessing the AI in the background)	Descriptive statistics from evaluators data: Agreement between initial human evaluator doses (data point #1) and AI decisions (data point #2), and between AI decisions (data point #2) and actual doses given to patients (data point #3). Proportion of AI decisions (data point #2) classified as appropriate / possibly too low / possibly too high Proportion of human decisions (data point #3) classified as appropriate / possibly too low / possibly too high
AI decisions evaluation	Quantitative analyses of AI decisions: estimate patients' outcomes if the AI decisions were followed and compare them to actual outcomes (which were linked with human decisions). We will use 2 methods: 1) compare short-term outcomes between model-concordant treatment and model-non-concordant treatment, with confounder adjustment; 2) off-policy policy evaluation of the AI policy in the prospective ICHT cohort.

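### The primary objective is to confirm availability and acceptable lag, but no result would count against it, and the named summaries (average lag, response delay) can hide late or missing outputs

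*Protocol*

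**What the plan says.** The primary objective (Section 2) is to "Confirm operational robustness and technical reliability of the software when operating in real-time in an operational ICU environment". The matching hypothesis (Section 1.2) is that the system can be run with "high availability, reliability and acceptable lag", the lag being near real-time. The protocol puts no number on *high* or *acceptable*.

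Section 2 gives two example indicators. For availability it is "what percentage of time is the system available, at different times of the day and night, on weekdays versus weekends, etc". For lag it is "delay between data recorded at the bedside and model producing an output".

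Section 3 lists what is logged automatically: the time from a clinical event to its record in the database, system accesses, and server status with outages. A separate online form captures faults that users meet, and is kept apart from the system so that an outage cannot affect it.

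The outcome table in Section 3.1 has three system items: the percentage of data fields available, system availability expressed as the time taken to respond, and the count and type of technical faults.

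For all of this, Section 7 plans "Simple descriptive statistics (e.g. average system lag, number of technical issues per week", followed by an ellipsis.

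The protocol's only lag figure is in Section 3. It describes the duplicate ICCA database or the EPIC record, which holds "ICU patient data in near real time (estimated lag of 5 to 15" minutes).

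**The concern.** Confirming something implies that the data could have failed to confirm it. Here no level of uptime, lag or fault count is named as too poor, so any observed value can be reported as meeting the objective.

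The summaries that are named make this worse in two ways. Delays are usually skewed to the right, and an average says little about how often an output is seriously late. Delay is also measured only on outputs that were produced. If availability is expressed as a delay, as in Section 3.1, a request that got no answer drops out of the measure meant to detect it.

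This is the primary question. Section 1.1 describes a later stage in which recommendations are shown to clinicians, and this study supplies reliability evidence ahead of it. In the present study the outputs are hidden from the treating team, so no patient's care depends on a late one. What is at stake is the strength of the conclusion.

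**Working it through.** **Which lag is meant.** Three places describe different quantities:

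- Section 2: bedside record to model output (end to end).
- Section 3, automatic logging: clinical event to database record (roughly the input part).
- Section 3.1: time to produce a response, filed under availability (the processing part).

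Only the Section 2 quantity matches the objective, and the Section 3 list names no timestamp for the model output. The 5 to 15 minutes belongs to the input part. The protocol gives no inputs behind that estimate, so it cannot be reproduced.

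**What an average can hide.** The protocol has no lag data, so the distributions below are assumptions.

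- Two-point mixture: mean = 0.8 × 5 + 0.2 × 30 = 4 + 6 = 10 minutes, with one output in five at 30 minutes.
- In general, if the other lags are all 5 minutes, the share late = (mean − 5) / (late lag − 5):
  - mean 10, late lag 60: 5/55 = 9.1%
  - mean 15, late lag 60: 10/55 = 18.2%
  - mean 15, late lag 120: 10/115 = 8.7%
- Log-normal lags with mean 15 minutes and log-SD s have log-mean ln 15 − s²/2. For s = 0.5, 1.0 and 1.5, the share above 60 minutes is 0.1%, 3.0% and 4.7%. The same mean therefore fits very different tails.

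**Outputs that never arrive.** Let m be the share of expected outputs not produced. The mean over produced outputs does not contain m, so it stays at 10 minutes in the first example whatever m is. The share delivered on time does depend on m: for any limit from 5 to just under 30 minutes it is (1 − m) × 0.8. With m = 0 it is 80%; with an assumed m = 10% it is 0.9 × 0.8 = 72%.

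**How wide the word *high* is.** A 30-day month has 720 hours, so downtime = (1 − uptime) × 720:

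- 90% uptime: 72 hours
- 95%: 36 hours
- 99%: 7.2 hours
- 99.9%: 0.7 hours

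Nothing in the protocol says which of these would be too much.

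**Whether a share can be estimated.** Section 3 expects at most 600 to 1,500 evaluation data points (100 per user × 6 to 15 users). Suppose each carries one output, observations are independent and the true share on time is 95%. The 95% half-width is then 1.96 × √(0.95 × 0.05 / n): 1.7 percentage points at n = 600 and 1.1 at n = 1,500. Clustering by patient, site or outage would widen this.

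**The case against.** The strongest reply is that a reader might infer that the primary objective is judged by average lag alone, and the protocol does not say so. The average in Section 7 is one example in an open list. Section 2 names percentage uptime by day and night and by weekday and weekend, Section 3 logs outages, and Section 3.1 counts faults. A system that was down every night would show in those data. This stands, and it limits the point: the information is largely collected, but no value of it is defined as unsatisfactory.

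A reader might also infer that the 5 to 15 minutes is a ready acceptance limit. It is not. It is an expected delay for the data feed, it is a range, it excludes model processing, and it says nothing about availability. Comparing the 10-minute example with it would set outputs against a feed estimate.

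Thirdly, percentiles and intervals are commonly left to an analysis plan, which is not at hand, and the wording in Section 7 excludes none of them. That is fair, and a missing threshold taken alone could be treated as missing detail. However, the verb and the claim are the protocol's own, as is an availability measure that cannot register silence. Those are choices made in this document, and better ones cost little.

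**Conclusion.** The point holds in a limited form. The protocol sets out to confirm high availability and acceptable lag without any result that would count against either. The one lag summary it names is insensitive to late outputs, and its Section 3.1 definition of availability leaves out requests with no response. Section 2, Section 3 and Section 3.1 also describe lag differently.

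The size cannot be estimated, because the protocol has no lag or uptime data. The examples show only what is possible: a mean of 10 minutes with 20% of outputs at 30 minutes, or a mean of 15 minutes with 18.2% at 60 minutes, all others being at 5 minutes. They do not show that the system behaves this way.

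The documents do not support the conclusion that night-time or weekend failure would go unseen, or that 15 minutes is the protocol's own pass mark. This is an inexpensive improvement to the primary analysis and does not invalidate the study.

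**What to change.** - **Section 2:** keep bedside record to model output as the single primary lag. Reconcile the logging list in Section 3 and the outcome table in Section 3.1 with it; the other two delays can stay as labelled components.
- **Section 3.1:** define availability as the percentage of time the system is available, and list response delay under lag.
- **Section 7:** replace average lag with the median, the 95th percentile and the share of expected or requested outputs delivered within a prespecified limit. Count no output as a failure. Give a 95% interval, and use the day/night and weekday/weekend split that Section 2 already names.
- **Acceptable values:** fix the share and the uptime that count as acceptable before the 3-month interim dataset is opened. If the team does not wish to set them, change *confirm* to *describe* in the objective and word the hypothesis to match.
- **The 5 to 15 minutes:** use it only as a reference for the event-to-database delay.

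The cost is slightly more than wording. A timestamp for each model output may have to be added to the logs. The team must also define when an output is expected, since the only schedule stated in Section 3 is the 6-hourly screening. The reported figures may look less favourable than an average would.

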- 3- **Evaluation tab.** This is where the evaluation of the AI and human doctors’ decisions takes place. The option to scroll through the various previous time points is provided. The evaluation by the human evaluator takes place in several subsequent steps: First, the human evaluator makes a recommendation based on patient data alone (data point #1). Then, the human evaluator is presented with the AI recommendation (data point #2), along with other information (confidence in the suggested decision, explanation of why this action was recommended). They “rate” the AI decisions, by classifying the AI suggested actions in different categories, such as “likely safe”, “likely inappropriate”, “possible too low”, or “possibly too high”. Finally, the human evaluator is presented with the actual decision (made by human clinicians, data point #3) and the subsequent patient evolution (at least a few hours, but the final outcome of ICU death or survival will be presented if available). The human evaluators rate the actual decisions using the same scale, e.g. “likely safe”, “likely inappropriate”, etc. There will be a free-text box to enable the user to provide feedback on their decisions.

The software will be accessed on the dedicated laptop from within the NHS hospitals by off-duty clinicians enrolled in the study, whom we call “human evaluators”. To explore system’s usability around the clock, there will be no restrictions with regards to timing of the research, so the human evaluators will be able to conduct the research at any time and on any day of the week.

We intend to conduct the study during 1-hour sessions, during which the users will conduct these 2 actions:

- 1) Identify new patients for inclusion from a pre-screened list
- 2) Assess multiple decisions made on multiple included patients. Based on a conservative number of 5 patients with sepsis on each unit at any point in time, and between 4 - 10 sessions per user, we will gather a maximum of 600 to 1,500 data points (100 data points per user for 6 to 15 users). We expect to include an estimated

100 to 300 separate patients across 4 sites (based on 20 patients per month per unit and 27 months of total study period over the 4 units, which gives 540 potential eligible patients). This will enable to complete the study objectives.

Data about the system's operational reliability will be automatically collected:

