- Time elapsed between a clinical event (e.g., administration of a fluid bolus) and the record appearing in the database. This exploits the property of some clinical events to be time-stamped to quantify the lag in the system.
- Date and time of all system accesses
- Server status, down-time events, planned and unplanned outages. These events can be monitored remotely and logged by the ICT team.

An independent online form (survey-type) will be created to log all technical issues that the users may encounter (e.g., system unavailable, login issues etc). This survey will be kept separate from the system, so it can't be affected by server outage for example.

The data about the system's operational reliability and the technical issues reports do not contain patient sensitive information and will be available to researchers at Imperial College London, in the research groups of [name] and [name].

After running the study for 3 months on each study site, an interim analysis will be performed to test the data quality. A pseudo-anonymised dataset including the fields described in section 3.1 "study outcome measures" of all patients included so far in the study will be created. All patient identifiable information will be removed, patient NHS number will be replaced by an ad-hoc random number, and the mapping between the patients' true identity and identifiers will be kept on the NHS server. No patient health records will leave NHS systems.

The final analysis will occur at the end of the study period (after month 18, in August 2022), once all data has been collected. The pseudo-anonymised dataset will be transferred encrypted to an Imperial College London secured server, within the [name] Lab. Researchers in [name] and [name] groups will then conduct various modelling and analyses to assess the AI suggested decisions.

This trial will be conducted across four intensive care units: Imperial College Healthcare Trust - Charing Cross Hospital, Hammersmith Hospital, St Marys Hospital and University College London Hospital. All four units are capable of treating critically ill patients.

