#### For evaluators:

ICU doctors at the senior registrar, ICU fellow or consultant level

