### For both patients and evaluators:

Declined participation

No patient consent is required

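### Nothing separates evaluators from patients they treat, so rating one's own decisions and carrying AI advice into later decisions on the same patient both remain possible

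*Protocol*

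**What the plan says.** Section 1.1 describes shadow mode as running the tool while its result is not "provided to duty clinicians in charge of patient care". The third hypothesis in Section 1.2 repeats the condition: the AI decisions are ones "which remain hidden from on duty doctors".

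Section 3 states who sees the output: "we will include 6 to 15 ICU doctors, mixing senior registrars, ICU fellows and consultants". The users are "off-duty clinicians enrolled in the study", working on a dedicated laptop inside the hospitals, and "there will be no restrictions with regards to timing of the research". The evaluator first gives a dose from the patient data (data point #1), then sees and rates the AI dose with its confidence and explanation (#2). Last, the evaluator sees and rates the dose actually given (#3), together with at least some hours of what happened next.

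Eligibility for evaluators in Section 4.1 is "ICU doctors at the senior registrar, ICU fellow or consultant level". The one exclusion in Section 4.2 that applies to them is "Declined participation". Among the automatically collected operational data, Section 3 lists "Date and time of all system accesses".

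**The concern.** Off duty describes a doctor at a given hour; it does not define a separate group of people. A doctor who opens a case one evening could, within the protocol, be responsible for the same patient on a later shift. The doctor could equally have set the dose now presented for rating.

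The evaluator data and one of the two outcome methods would be affected. Data point #1 is meant to be an independent opinion, and the rating of #3 is meant to be an outside view of bedside care. The comparison of concordant with non-concordant treatment is meant to use bedside decisions made without sight of the AI dose. If treating doctors and evaluators overlap on the same patient and nobody records it, none of these can be taken at face value, and the overlap cannot be removed afterwards.

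**Working it through.** No figure in the protocol depends on this point, so the check is mainly a reading of the text, with a short count of sessions.

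**1. Is there any separation rule?** The places that could hold one are:
- *Eligibility (4.1, 4.2):* grade and refusal only; nothing on involvement in the patient's care.
- *Place (3):* inside the study hospitals; no allocation of cases to another unit or Trust.
- *Time (3):* off duty while using the system; otherwise unrestricted, with no waiting period.
- *Record (3):* date and time of access; the text does not say that the log holds the evaluator and the patient opened, or whether the evaluator was involved in care.

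**2. Can the patient still be in ICU?** Yes. The data feed lags by an estimated 5 to 15 minutes, and new admissions are screened every 6 hours. Sessions are planned around 5 sepsis patients present on a unit, and ICU outcome is shown only where it is already known.

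**3. Which decisions can a viewing affect?** Let a dose be given at time t and rated in a session at time s. The last rating step shows at least some hours of later course, so s is after t. That viewing cannot have changed the dose at t. A dose given at a later time u > s, by or under a doctor who attended that session, can be affected.

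**4. Which analyses in Section 7 are touched?**
- *Agreement of #1 with #2:* #1 may be a recalled own decision.
- *Ratings of #3:* may be self-ratings.
- *Agreement of #2 with #3:* may rise through carry-over into later decisions.
- *Outcome method 1 (concordant versus non-concordant):* may mix AI-informed with independent decisions. Confounder adjustment cannot separate them unless exposure is recorded.
- *Outcome method 2 (off-policy evaluation):* not directly dependent. It needs an estimable behaviour policy, overlap and measured confounders, not clinicians who are unaware of the target policy.
- *Primary objective (availability, reliability, lag):* not touched.

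**5. How much viewing is planned?** Section 3 gives 6 to 15 evaluators and 4 to 10 sessions each:
- Sessions: 6 × 4 = 24 to 15 × 10 = 150.
- Patients opened per session are not stated. Assuming 1, there are 24 to 150 patient viewings. Assuming all 5 on one unit, there are 24 × 5 = 120 to 150 × 5 = 750.
- The study expects 100 to 300 patients.

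These are viewings, with repeats, not distinct patients and not exposed decisions. They show only that the possibility need not be confined to a handful of patients. The share of exposed decisions would also need the rota, the units on which evaluators work, and the fraction of each patient's decisions that follow a viewing. The protocol gives none of these.

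**The case against.** The strongest reply is that the protocol meets its own definition. Shadow mode is defined by what reaches duty clinicians, and evaluators are off duty throughout. Carry-over needs an evaluator to be on the same unit's rota and to treat the same patient later in the same stay, and the protocol states neither. The remark in Section 8.2 that local staff identify patients concerns confidentiality and does not place evaluators on the units they rate. Section 3 also attributes the doses given to nurses as well as doctors, so a senior doctor's presence on shift does not make each dose theirs. Section 7 plans only descriptive statistics for the ratings.

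Much of this stands, and it rules out several stronger readings:
- *That shadow mode is broken.* The text leaves a route open; it does not show that anyone takes it.
- *That AI-to-actual agreement is inflated, or that self-ratings favour the bedside doctors.* Both are possible. Neither their frequency nor the direction of the self-rating effect can be derived from the document, and no direction of bias is established for method 1 either.
- *That both outcome methods fail.* Off-policy evaluation does not require blinded clinicians.
- *That a large share of decisions is exposed.* With an assumed rota of 10 to 20 senior doctors per unit, 6/4 = 1.5 to 15/4 = 3.75 evaluators per unit would cover 1.5/20 = 7.5% to 3.75/10 = 37.5% of senior shifts. That counts shifts worked by any evaluator, including those who never opened the patient concerned. On the same assumption, one viewer covers 1/20 = 5% to 1/10 = 10% of later shifts, and doses before the viewing are unaffected.

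The reply does not supply a rule. Same-unit working is the natural reading of on-site evaluators who also enrol new admissions, and nothing excludes it. Nor can this be left wholly to an analysis plan. Who may open which case is a protocol and software rule, and a sensitivity analysis is possible only if exposure has been recorded.

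**Conclusion.** The point holds as a gap in the design. The protocol states a blinding condition, and its procedures secure it only for the length of a session. Followed as written, it permits self-rating of #3, a recalled own decision as #1, and carry-over of AI advice into later decisions on the same patient. The consequences fall on the evaluator data and on outcome method 1, all of them secondary. The size is unknown: 24 to 150 sessions are planned, but the share of exposed decisions cannot be computed from the document. The conclusion assumes that some evaluators work clinically on the units whose cases they open, which the protocol neither states nor excludes. If evaluators are in fact drawn from other units, a sentence saying so would largely settle the matter.

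**What to change.** - In Sections 3 and 4.1, state that an evaluator may not open the evaluation tab for a patient they have treated, or expect to treat, during that ICU stay. Assigning cases from another unit is one way to do this. The rule limits access to the research tool and changes nothing in patient care.
- State that the access log records the evaluator and the patient opened, as well as date and time.
- Flag decisions made after a viewing while that viewer was on duty for the patient's unit. Section 8.3 keeps clinician identities within Trust systems, so the linkage to the roster should be done there and only the flag released. A roster shows who was on shift, not who set a dose, so the flag will be somewhat over-inclusive.
- Report the agreement and concordance analyses with and without flagged decisions.

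The cost is some lost evaluator-patient pairs, one access rule in the software and a small linkage task. Holding ratings until ICU discharge would be a stricter option, but it would remove evaluation of current patients and is not required.
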